For informed consent procedures, we will follow the 1991 Code of Federal Regulations (45 CFR 46.102) that defines "research" as a systematic investigation designed to develop or contribute to generalizable knowledge. Guiding principles include respect for persons, beneficence, and just selection of research subjects. The informed consent process will conform to these policies and to UCLA's consent form standards, including the handling and processing of anonymized genetics specimens, and the process will be reviewed and approved by the UCLA IRB.

Two-week Placebo+CM Lead-in Period: After providing written informed consent, participants will begin a two-week (six-visit) outpatient lead-in period during which they will attend the outpatient research clinic thrice-weekly and complete a comprehensive assessment of their baseline drug use and psychological/medical status, including a medical history and physical exam, EKG, labs, HCV and HIV serotyping, and other study measures (see Measures below). An EKG will be repeated if results indicate a corrected QT of > 450 msec in men or > 460 msec in women (see below). Participants will complete a neurocognitive battery on the final week of the lead-in period as described below. All participants will take placebo capsules twice daily during the lead-in period. The placebo capsules will contain riboflavin which will be used to assess participants' ability to adhere to medication taking. Participants will be allowed one urine specimen during the lead-in with a riboflavin concentration less than 900 ng/ml as measured via UV fluorescence, but any participant with more than one of the five (excluding the day of consent) possible urine samples below the 900 ng/ml threshold will be considered medication non-adherent and will not be eligible. In addition, subjects must provide at least one MA positive urine drug screen during the lead-in period. The two-week lead-in period may be extended at the discretion of the PI in limited cases, including telephone consents, holidays, etc.

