Experimental Drug Procedures: Experimental medication will be obtained from MediciNova. The study drug is Ibudilast (MN-166, previously known as AV411) and the product is delayed-release Pinatos® capsules, the Japanese generic IBUD product produced by Taisho Pharmaceuticals and imported by MediciNova. Matching placebo capsules will also be supplied by MediciNova. The doses

used to date have been 10 mg strength and formulation modification to 20-50 mg dosage strengths are in process. Should this protocol involve dosing at strengths greater than 10 mg, then supportive documents/amendments would be filed in advance of the change. In addition, all participants will also take a daily dose of 25 mg riboflavin for assessment of medication adherence via urinary riboflavin (Herron, Mariani et al. 2010), one capsule in the AM and one capsule in the PM each containing 12.5 mg riboflavin (details under adherence monitoring below). All capsules will be prepared by our research pharmacy. Upon receipt of a prescription signed by the study clinician, the un-blinded pharmacist prepares and sends a supply of study medication in blister packaging to the study clinic. . After randomization, participants will take the first dose of study medication at the research clinic under observation by the study clinician after which study medication will be dispensed to participants for self-administration at home. Participants will then meet with a study clinician and exchange the empty blister package for a new blister package. Participants will be in possession of the current week and next week's medication supply so that they will not run out of medication in the event that they miss one of the medication dispensing visits. Unused medication will be recorded for the pill count and will be sent for incineration after the conclusion of the trial. Additional details concerning medication adherence procedures are detailed below.

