- Study medication will be dispensed in **blister packages**, which have been shown to be an effective intervention to promote adherence (Haynes et al., 2005). Participants will receive \$5 in gift cards for bringing their medication blister package to the clinic each week for a medication adherence pill count performed by study staff. Any non-adherence will be addressed by the clinician in the weekly medication adherence counseling sessions. Participants will be instructed to leave any unused medication in the blister package such that participants' self-reported pill-taking behaviors can be reconciled with the remainder of pills in the take-home blister packet. In addition to IBUD or placebo capsules, participants will take one capsule containing 12.5 mg **riboflavin** twice daily (total of 25 mg daily if the participant is adherent to both the AM and PM doses). At each study visit, urine specimens will be analyzed via fluorimetry for quantitative measurement of riboflavin as an objective measure of medication adherence during study data analysis. Urine specimens with a riboflavin concentration greater than or equal to 900 ng/ml will be considered positive and indicative of medication adherence (Herron, Mariani et al. 2010). We use 25 mg riboflavin instead of 50 mg as 25 mg is less likely to spill over in the urine past 24 hours and is therefore more accurate in detecting recent medication ingestion (Herron, Mariani et al. 2010). The study clinician will feed back riboflavin results to participants at each visit and counsel participants regarding any negative riboflavin results.
- An aliquot (5 ml) from each of the twice-weekly urine specimens during the 12 week medication period will be collected for measurement of concentrations of IBUD and its primary metabolite (6,7-dihydrodiol-ibudilast) as a "snapshot" **biological assessment of medication adherence** during the trial. One sample will be collected immediately prior to starting study medication (negative control). In addition, one serum sample (10 ml blood) will be collected from participants during week 3 of the study medication period for measurement of serum IBUD and 6,7-dihydrodiol-ibudilast levels. Samples will be frozen and stored until analysis is performed. The study day and time of collection will be recorded. The subject will be asked to provide the time that they took their last dose of study medication before providing the sample.

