Examination of potential confounders Rates of adverse events and medication adherence in the IBUD and placebo groups will be calculated and compared. Medication adherence will be assessed as a continuous variable: the proportion of twice-weekly urine drug samples positive for riboflavin (≥ 900 ng/ml riboflavin as determined via quantitative fluorimetry), and as a dichotomous variable: medication adherent ($\geq 80\%$ of twice-weekly urine drug screens positive for riboflavin). Adherence will also be assessed via qualitative measurement of IBUD and metabolites in urine and serum samples, which is the gold standard for assessing adherence in the IBUD group but is limited by the fact that assessment of adherence in the placebo group is not possible. Models for MA use outcomes will be repeated including the continuous measure of adherence as a co-variate. The models will also be run with the sample stratified as medication adherent versus non-adherent. As pre-treatment abstinence is an important predictor of treatment outcomes and medication response in stimulant dependence trials (Elkashef, Rawson et al. 2008, Bisaga, Aharonovich et al. 2010), the sample will be stratified by ability to achieve initial abstinence with CM during the two-week lead-in period to explore whether medication effects may differ in these subgroups.

Aim 2: To determine whether IBUD results in longer treatment retention than placebo among MA dependent participants.

Hypothesis 2: IBUD will result in significantly greater treatment retention than placebo

Analysis: The mean number of days retained, defined as the number of days from the start of study medication to the final clinic visit during the 12 week treatment period, will be compared for IBUD versus placebo via t-test. Cox proportional hazards model will be used to compare days retained for IBUD versus placebo controlling for co-variables including age, gender, and baseline MA use. These analyses will then be repeated with the sample stratified by ability to achieve initial abstinence with CM during the two-week lead-in period to explore whether medication effects may differ in these subgroups.

The following exploratory HIV-related aims will be address in the HIV positive participants.

Aim 3: To determine whether IBUD improves biological (CD4 count; HIV RNA) and neurocognitive outcomes more than placebo among HIV-positive MA dependent participants.

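### During treatment the riboflavin marker is in a separate capsule from the study drug, yet the plan's adherence variables rest on riboflavin alone, so a participant who omits study capsules can be classed as adherent

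*Combined protocol and SAP*

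**What the plan says.** **Lead-in.** In the section on the Two-week Placebo+CM Lead-in Period, marker and test capsule are one object: "The placebo capsules will contain riboflavin which will be used to assess" adherence to capsule-taking.

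**Treatment phase.** The arrangement changes. Medication Adherence Support/Monitoring states: "In addition to IBUD or placebo capsules, participants will take one capsule containing 12.5 mg" of riboflavin, twice daily. Experimental Drug Procedures likewise adds riboflavin to the study regimen, as "one capsule in the AM and one capsule in the PM each containing 12.5 mg riboflavin". After the first dose, which is observed in clinic, capsules are taken at home.

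**Specimen rule.** A urine at or above 900 ng/ml riboflavin "will be considered positive and indicative of medication adherence".

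**Participant rule.** Under Aim 1, Examination of potential confounders, the continuous measure is the proportion of twice-weekly urines that are riboflavin-positive. The dichotomous measure requires at least 80% "of twice-weekly urine drug screens positive for riboflavin". The continuous measure enters repeat models of MA use as a covariate. For the dichotomous one, "The models will also be run with the sample stratified as medication adherent versus non-adherent". The Research Plan lists adherence level among the pre-specified subgroups.

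**Other adherence data.** Blister-pack pill counts are made in both arms. A urine aliquot is stored at each twice-weekly visit, and a serum sample is taken in week 3, for ibudilast and its metabolite. The analysis section calls the assay the gold standard in the IBUD arm and notes that it cannot assess the placebo arm. Neither source enters the adherent versus non-adherent class, and no rule covers disagreement between them and riboflavin.

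**The concern.** A tracer measures ingestion of whatever carries it. In the lead-in, riboflavin tracks the capsule whose intake is being tested. In the treatment phase it tracks a companion capsule, and study-drug intake has to be inferred. The analysis section acknowledges the assay's limitation in the placebo arm but not this one.

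Omitting study capsules while still taking riboflavin is possible in practice. Participants are told about riboflavin monitoring (Counseling Procedures), can be excluded on it in the lead-in, and hear their riboflavin result at each visit. They know which marker is being checked.

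At stake are the analyses meant to describe the drug effect in people who took the drug, and the comparison of adherence between arms. If unexposed IBUD participants are counted as adherent, the effect in that stratum is diluted, and the riboflavin-based adherence rate overstates exposure. Counseling Procedures itself calls non-adherence a severe threat to the validity of a medication trial, so the measure deserves a definition that refers to the study drug.

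**Working it through.** The plan gives no figure to reproduce here. The check applies the stated rule to the stated schedule.

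**Inputs**
- Treatment lasts 12 weeks with two visits a week: 12 × 2 = 24 scheduled specimens.
- Study drug is taken twice daily: 12 × 7 × 2 = 168 scheduled doses.
- The threshold for *medication adherent* is 80% of specimens riboflavin-positive.
- The first study dose is observed; later doses are not.

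**Step 1: positives needed.** 0.80 × 24 = 19.2, so 20 are required. 20/24 = 83.3% passes; 19/24 = 79.2% fails. The text does not say whether the denominator is scheduled or available specimens. I use the 24 scheduled; the case in Step 2 passes either way.

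**Step 2: a participant who takes only riboflavin.** Suppose every riboflavin capsule is taken, each specimen reaches the threshold, and no study capsule is taken after the observed dose.
- Riboflavin score: 24/24 = 100%, at or above 80%, so the class is *adherent* and the continuous covariate takes its maximum of 1.
- Study doses taken: 1/168 = 0.6%.

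**Step 3: would other planned data change the class?**

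| Measure | Arms | Would show the omission? | Enters the adherent class? |
|---|---|---|---|
| Urine riboflavin | Both | No | Yes, alone |
| Study-capsule pill count | Both | Yes, unless capsules are discarded | No |
| IBUD/metabolite in urine and serum | IBUD only | Yes | No |

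The omission can be seen in data already planned, but the class that stratifies the models ignores those data.

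**Step 4: effect on the stratum, by assumption only.** Let *f* be the share of the IBUD *adherent* group who took essentially no drug. If they respond as on placebo and are otherwise comparable, the risk difference in that stratum is multiplied by (1 − *f*). Assume 42 truly adherent IBUD participants. Adding 7 who took only riboflavin gives *f* = 7/(42 + 7) = 14.3%; adding 14 gives 14/(42 + 14) = 25%. None of 42, 7 or 14 comes from the documents. They show how the formula behaves and are not estimates.

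**The case against.** **No planned primary conclusion depends on this rule.** This stands. The primary outcome is compared by intention to treat. The adherence split is secondary, and its strata are formed after randomization, so even perfect measurement would give only weak evidence about efficacy under full exposure.

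**The IBUD assay already covers the gap in the IBUD arm.** This largely stands. A reader might infer that a difference in exposure would go unnoticed. The documents do not support that, because twice-weekly urine aliquots and a week 3 serum sample are planned for exactly this purpose. What remains is that a participant shown by assay to be unexposed still sits in the *adherent* stratum.

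**Omission need not fall mainly in the IBUD arm.** This also stands. Dose Justification names nausea as the most common side effect, which makes a differential tempting to infer. But in the plan's own phase I table, gastrointestinal upset was reported by 4 of 11 on placebo and 4 of 11 on 50 mg BID. That sample is too small to exclude a difference, but it does not show one. Participants are also asked to report side effects, and dose reductions are permitted.

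**The text might mean co-encapsulation.** Experimental Drug Procedures says "All capsules will be prepared by our research pharmacy", and its riboflavin sentence alone could be read that way. The adherence section's wording points to a separate capsule. If practice differed, one clarifying sentence would close the point.

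**Pill counts can be defeated.** True: capsules can be removed and discarded. A combined rule reduces misclassification without eliminating it.

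**Conclusion.** The concern holds as a defect in the definition of a secondary variable. Both adherence variables measure riboflavin capsule-taking, and the 80% rule can be met in full by someone who takes no study capsule after the observed first dose. The defect reaches the adherence-stratified and adherence-adjusted models of MA use and the riboflavin-based comparison of adherence between arms. If the same variable is intended there, it also reaches the exploratory Aim 3 regression, which lists adherence as a covariate. It does not reach the primary comparison.

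Its size is unknown. The documents give no frequency of selective omission, so neither a dilution percentage nor a direction of imbalance between arms can be stated as a finding. The 14.3% and 25% above depend wholly on assumed counts. The conclusion rests on reading the treatment-phase riboflavin as a separate capsule, as the adherence section states.

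**What to change.** Amend Examination of potential confounders as follows.

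1. **Class.** A participant is medication adherent only if both conditions hold, in both arms: at least 80% of twice-weekly urines riboflavin-positive, and a study-capsule pill count of at least 80% of the capsules prescribed at the time. The pill-count denominator follows permitted dose reductions and holds. State how unreturned packs are counted, and whether the 80% riboflavin denominator is scheduled or available specimens.
2. **Sensitivity analysis.** Repeat the stratified models with the riboflavin-only class.
3. **Check on the marker.** In the IBUD arm, report the proportion of riboflavin-positive specimens, collected while study drug was prescribed, that contain no detectable ibudilast or metabolite. Use the stored aliquots and state the detection limit. Keep this descriptive, so that the class stays the same in both arms.

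The first two items are SAP wording applied to data already collected; the third uses an assay already planned. The costs are somewhat fewer participants classed as adherent, hence smaller strata, and some misclassification remaining because pill counts can be manipulated. I would not ask for riboflavin to be put inside the study capsule: the drug is an imported delayed-release product with supplied matching placebo, so that would be a formulation change.

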Drug use disorders commonly follow a history of experiencing high levels of early-life stress (ELS) (Repetti, Taylor et al. 2002, Dube, Felitti et al. 2003, McFarlane, Clark et al. 2005, Cohen, Paul et al. 2006), which have been linked with neural dysfunction (Cohen, Grieve et al. 2006, Seckfort, Paul et al. 2008, Baker, Williams et al. 2013, Philip, Sweet et al. 2013). HIV and high ELS have combined pathological effects on brain morphometry and neurocognitive function in HIV+ patients (Clark, Cohen et al. 2012). MA abuse and high ELS have some common effects, both involving upregulation of neuroinflammatory processes. High levels of ELS also are associated with increases in pro-inflammatory cytokines (Pollitt, Kaufman et al. 2007, Carpenter, Gawuga et al. 2010, Slopen, Lewis et al. 2010). These findings suggest that high ELS may exacerbate MA-related neuropathology in HIV+ patients and therefore we will explore potential effects of ELS on treatment outcomes as well as interactions with ibudilast treatment. As recent stress and/or trauma may confound any associations between ELS and neuroinflammation or cognition, we will assess recent stress and trauma using the Perceived Stress Scale (PSS-14) and the Posttraumatic Stress Disorder Checklist - Civilian (PCL-C) and control for these in our analyses.

Research Plan

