Concomitant Medications: All subjects will be asked about concomitant medications weekly during the lead-in and outpatient treatment period. Concomitant medications include both OTC and prescribed medications.

Early Life Stress Questionnaire (ELSQ): The Early Life Stress Questionnaire (McFarlane, Clark et al. 2005) (ELSQ) is a self-report questionnaire that considers 19 adverse life events (crime, sexual abuse, family conflict, bullying, etc.). High ELS is defined as exposure to ≥ 3 ELS events prior to age 19 (Cohen, Paul et al. 2006, Paul, Henry et al. 2008, Seckfort, Paul et al. 2008, Clark, Cohen et al. 2012), consistent with the rates of ELS in the general population (Cohen, Paul et al. 2006). Previous studies (Cohen, Grieve et al. 2006, Cohen, Paul et al. 2006, Seckfort, Paul et al. 2008, Clark, Cohen et al. 2012) have shown that using a cut-point of ≥ 3 ELS events provides the greatest discrimination on the basis of ELS for behavioral and neural measures. The ELSQ will be administered during week 3.

Perceived Stress Scale (PSS-14): The PSS-14 is a validated, self-report questionnaire that assesses the extent to which individuals perceive their life to be stressful (Cohen and Williamson 1988). The PSS-14 will be administered during baseline.

Posttraumatic Stress Disorder Checklist - Civilian version (PLC-C): is the most commonly used self-report questionnaire assessing number and severity of PTSD symptoms. The PLC-C will be administered during week 3.

Genotyping/SNP: 10 ml whole blood will be collected at baseline for DNA extraction for genotyping analyses.

Hamilton Depression Rating Scale (HAMD) (Riskind, Beck et al. 1987): Completed in just 5 to 10 minutes, the HAMD can be used to quickly evaluate symptom severity, to confirm a diagnosis of depression, to explore depressive symptoms, and to measure treatment outcome. The HAMD will be administered during the lead-in period and weekly during the medication and follow-up phase.

HIV CD4 Count and Viral Load: Participants who are HIV+ will have CD4 count and viral load measured at baseline, at the termination of medication (week 13), and at the last follow-up visit (week 16).

HIV medication adherence: Participants who are HIV positive will have their HIV medication adherence assessed monthly by asking them to estimate the proportion of their medications that they took in the past month.

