Exploratory analyses Baseline neurocognitive functioning of participants will be described using results of the neuropsychiatric (NP) battery performed at baseline. Baseline to post-treatment changes in scores on tests in the NP battery will be calculated for IBUD and placebo groups. Effect sizes for IBUD on NP battery change scores will be calculated and used to determine whether future fully powered studies examining NP changes with IBUD are warranted. In addition, GEE models will be used to compare change in the brief serial weekly cognitive assessments (Balloon Analog Reaction Time task and Stop Signal test) during treatment with IBUD versus placebo. To explore whether severity/type of neurocognitive dysfunction at treatment entry mediates response to IBUD, baseline scores on NP assessments will be included as co-variables in the models assessing IBUD effects on MA use outcomes and treatment retention. Finally, potential effects of polymorphisms in dopaminergic genes and GDNF (Yoshimura, Usui et al. 2011), as well levels of inflammatory biomarkers and neurotrophic factors on treatment outcomes will be explored. The sample will be stratified by genotype for each SNP and changes in MA use and retention for IBUD versus placebo will be compared in these sub-groups. In addition, baseline versus post-treatment serum and plasma levels of inflammatory markers neurotrophic factors will be compared for IBUD versus placebo groups and by HIV serostatus. Correlation between early life stress measures and baseline severity of MA abuse as well as treatment outcomes, including potential early life stress-ibudilast interactions, will also be explored.

We recognize that the study is not powered to detect statistical significance in these analyses, especially if corrections for multiple testing are employed (Benjamini and Hochberg 1995) and as a result these analyses are by design for exploratory purposes only. Still we feel that including these probes of potential IBUD mechanisms of action within the context of this early clinical trial is important in that the results may bolster any observed effects of IBUD on MA use outcomes and direct the design of subsequent adequately powered confirmatory phase III trials.

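### Early-life stress and PTSD symptoms are first measured at week 3 of study medication, so the exploratory early-life stress analyses lose early leavers and risk a post-randomisation covariate

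*Combined protocol and SAP*

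**What the plan says.** Three stress instruments are described under Study Measures and Assessments. For the early-life stress questionnaire, "The ELSQ will be administered during week 3". For the PTSD checklist (spelled PCL-C in the Background and PLC-C here), "The PLC-C will be administered during week 3". For perceived stress the timing differs: "The PSS-14 will be administered during baseline".

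The Appendix II schedule matches. The ELSQ and PTSD checklist appear only at week 3 of the medication phase, with no baseline mark, while the PSS-14 has a baseline mark.

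Two places describe how the scores will be used:

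- **Background, last paragraph.** The authors state that "we will explore potential effects of ELS on treatment outcomes as well as interactions with ibudilast treatment". They add that recent stress and trauma will be assessed with the PSS-14 and the "Posttraumatic Stress Disorder Checklist - Civilian (PCL-C) and control for these in our analyses".
- **Data Analysis, Exploratory analyses.** Early-life stress is to be correlated with baseline MA severity and with treatment outcomes, including "potential early life stress-ibudilast interactions".

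**The concern.** A predictor or effect modifier of a randomised treatment is best measured before randomisation. Here two of the three stress measures are taken after it, with two separate consequences.

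- **Selective missingness (both instruments).** A score exists only for people still attending at week 3. Leaving early is itself part of what the trial measures: retention is the Aim 2 outcome, and a participant without urine results in weeks 11 and 12 counts as non-abstinent. The early-life stress analyses therefore omit people because of something closely linked to both outcomes. Even the correlation with baseline MA severity loses them.
- **Post-randomisation covariate (PTSD checklist only).** The checklist records current symptoms. By week 3 these may reflect study drug as well as MA use or withdrawal. Adjusting a treatment or interaction effect for such a score may change what that effect means.

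The second problem does not extend to the ELSQ in the same way. High early-life stress is defined by events before age 19, which treatment cannot alter, although recall might vary. For the ELSQ the issue is who has a value.

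**Working it through.** No stated figure rests on this timing, so there is none to reproduce. The check sets the relevant sections side by side and adds simple arithmetic.

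**1. Week 3 falls after randomisation.** Appendix II puts it in the medication phase, and the adherence section uses the same count for the serum sample ("during week 3 of the study medication period"). Randomization Procedures starts intention-to-treat entry at randomisation. Both questionnaires therefore come after about two to three weeks of assigned treatment.

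**2. People can be lost before then.** Termination and Follow-Up Procedures allows early termination after two consecutive missed weeks, which can be met before week 3. The drop-out tracking paragraph expects high attrition. Its off-site contact covers urine samples and weekly data, and the ELSQ and PTSD checklist are one-time forms. No section provides for giving them later or for handling their absence.

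**3. The loss is related to outcome.** Power calculations treats missing as non-abstinent. For retention, everyone with an early-life stress score has by construction stayed to week 3.

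**4. Size of the loss.** The documents give no drop-out rate to week 3, so a proportion *d* from 5% to 30% is assumed.

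Missing = 140 × *d*; available = 140 × (1 − *d*); standard-error inflation from the smaller number = 1/√(1 − *d*).

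| Assumed *d* | Missing | Available | SE inflation |
|---|---|---|---|
| 5% | 7 | 133 | 1.026 |
| 10% | 14 | 126 | 1.054 |
| 20% | 28 | 112 | 1.118 |
| 30% | 42 | 98 | 1.195 |

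The loss of precision is modest, about 3% to 20%. The table does not measure bias in the interaction. That depends on whether loss differs jointly by arm and early-life stress, for which the documents give no input.

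**5. The covariate, conditionally.** Suppose a model that estimates the treatment effect also adjusts for the week-3 PTSD score. In a linear approximation the adjusted effect is the total effect minus *k* × *b*, where *k* is the drug's effect on the score and *b* the slope of outcome on score, both in SD units. The documents give neither. With assumed *k* of 0.1 to 0.3 and *b* of 0.2 to 0.4, the shift is 0.1 × 0.2 = 0.02 to 0.3 × 0.4 = 0.12 SD. With *k* = 0 it is nil.

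**6. What a lead-in value would give.** Randomization requires that baseline data collection be complete. A lead-in ELSQ and PTSD checklist could therefore be available for up to all 140 randomised participants.

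**The case against.** Four counter-arguments carry weight.

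- **The adjustment has a narrower stated purpose.** A reader might infer that the plan adjusts the treatment effect on MA use for the week-3 PTSD score and so removes part of that effect. The documents do not say so. The Background justifies the phrase "control for these in our analyses" by possible confounding of early-life stress associations with neuroinflammation or cognition. The abstinence and retention models do not list the checklist as a covariate, and the sentence proposing interactions mentions no adjustment. This stands: the covariate problem is conditional on how a loosely worded intention is carried out.
- **The lead-in is already full.** It holds the SCID, ASI, several self-report scales, medical work-up and a 60-minute counselling session, and participants who do not finish baseline procedures within two weeks are not randomised. This is a real but small cost. The PSS-14 and the WURS, another retrospective childhood measure, already sit there, and since July 2016 the cognitive battery has been cut to the MoCA.
- **Week 3 coincides with a biomarker draw.** True, but markers are also drawn at baseline, and the protocol gives no reason for the timing.
- **A lead-in PTSD score would still reflect MA use or withdrawal.** Correct: the lead-in requires an MA-positive urine and pays for abstinence in its second week. Moving the checklist removes only possible influence of assigned treatment and loss after randomisation.

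The analyses concerned are also declared exploratory and not powered for significance. That limits the importance of the point but does not answer it.

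**Conclusion.** The point holds as a minor one. The timing is unambiguous, and it leaves early leavers without an early-life stress or PTSD score in analyses whose outcomes include retention and missing-as-failure abstinence. At an assumed 5% to 30% loss before week 3, between 7 and 42 of 140 would be affected; the true figure and its split by arm are unknown from the documents. The PTSD checklist becomes a post-randomisation covariate only if it enters a model that estimates a treatment or interaction effect, which the plan leaves open.

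Two stronger readings should be resisted. One is that the interaction estimate is biased by a known amount: re-expressing an overall success rate among those who reach week 3 would not show this. The other is that the trial's main result is compromised: the primary logistic model adjusts for age, gender, baseline MA use days and HIV status, none of which depends on these questionnaires.

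**What to change.** Move the ELSQ and PTSD checklist into the six-visit lead-in alongside the PSS-14, and amend the Study Measures and Assessments text and Appendix II to match. The cost is a schedule change and slightly more questionnaire time in a period that must be completed within two weeks.

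For participants who have only week-3 values:

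- report the number missing each score by arm;
- do not adjust treatment or interaction effects for the week-3 PTSD score;
- label the early-life stress analysis as restricted to those reaching week 3.

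The Exploratory analyses text should also state which models, if any, include the PTSD checklist. These steps need only text and reporting changes.
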